8.2. Accelerometer measurements

Accelerometers, ActiGraph GT9X Link, were placed on the non-dominant wrist of the Index Adult and Index Child during baseline and 12-month data collection visits. The participants were instructed to wear the accelerometers continuously for one week. The accelerometers are waterproof and thus did not need to be removed for any reason. After the participants wore the monitors for 7 days, they both (if the Index Child is between the ages of 10 and 12 years) completed a questionnaire (Global Physical Activity Questionnaire for the Index Adult and the Physical Activity Questionnaire for Children for the Index Child) via interview with the Data Collector over the phone. These questionnaires assessed level of physical activity during the same time the monitor is worn, so that the accelerometer data can be compared to the self-reported data.

8.3. Questionnaire measurements

Index Adults are assessed on dietary intake and physical activity via questionnaires. For dietary intake, validated food-frequency questions are administered to monitor intake of fruits, vegetables, and fats (NHIS 2000), sweetened drinks (NHIS 2005), and fast food (EAT study). Physical activity questionnaires include the Global Physical Activity Questionnaire (GPAQ), which provide contextual data to complement accelerometer data and provide information as to where activity is taking place (i.e., domains). The GPAQ will be calibrated with the accelerometer to improve data accuracy in a one-week post-data collection phone visit. Other data is collected, including demographic information, income and food insecurity information, medication usage and dose changes, health history information, substance use, depression screen, and related questions.

Index Children are assessed on dietary intake, physical activity, and screen time. These questionnaires are given to the Index Adults, and they answer the questions as proxy for the children. The Family Nutrition and Physical Activity tool (FNPA) is used, which is a child environmental measure developed in partnership with the American Dietetic Association to characterize behaviors related to childhood obesity. Validation shows a 1-point change is associated with a 0.1 change in BMI z-score, and the score correlates with cardiovascular risk indices. It measures changes emphasized by our intervention including decreasing sweetened beverages, sweet snacks, fast food and TV, and increasing family meals, family physical activity, and fruits and vegetables. The scale allows us to compare families who choose different goals and resources. Additional validated parent questionnaires were used to

assess child screen time, NCI quantitative FV screener and other dietary measures including sugar-sweetened beverages.

The Primary Food Preparer (PFP) of the household (who may be the Index Adult or a different household member) completes a validated survey on the availability of fruits and vegetables in the house and a questionnaire on how often the family eats together inside and outside the home or brings in take-out food. If the PFP is not the Index Adult they complete the same dietary measures as the Index Adult. Other exploratory measures include collecting BMI on the non-Index Adult PFP and other children residing within the household.

9. Data Analysis Plan

The trial design includes three factors: 1) two treatment groups (control, intervention), 2) four time points (0, 6, 12, and 18), and 3) two age groups (adult, child). Each variable will be summarized by descriptive statistics, including mean, standard deviation and quartile at each time point (separately by treatment and age groups). Index Adults and Index Children will be analyzed separately. Outcomes have repeated measures at multiple time-points. The primary analysis compares the change in primary outcomes from baseline to 12 months between the treatment groups to gauge the efficacy of the intervention. The secondary analysis compares both the 6- and 18-month average change from baseline between the two treatment groups to assess short-term effect and longer-term sustainability. The analysis will be based on intention-to-treat and use two-sided t-test for the primary outcomes with multiple imputation to account for missing values. Multiple imputation models will incorporate 6-month values when available. Linear mixed models for repeated measures will be used for other analysis using multiple time points.

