2. RCT

This RCT involves two arms, Education Only group (control) and the Health Coach group (intervention). Participants in the Education Only group receive educational materials on health family diet and activity (We Can booklets) and quarterly newsletters. In addition, they receive resource screenings at baseline and 6-months, follow-up phone calls using the Community Resource Specialist's screening questionnaire, and referrals to appropriate basic-needs resources.

Those in the Health Coach group received guidance from an assigned Health Coach, in which up to 5 in-person visits and 4 phone visits were completed within a 12-month period. MI was used during these sessions to help set goals based on the family's health needs and priorities. The Health Coach group participants received the same resource screening and newsletters as the Education Only group, but they also received additional resources to help their family's needs based on their goals made with the Health Coach.

Primary outcomes based on the 12-month intervention are separated by Index Adult and Index Child. For the Index Adult the primary outcomes are changes from baseline to 12-months in 1) BMI (kg/m^2), 2) the average minutes of moderate to vigorous activity, and 3) average hours of sedentary time per day. For the Index Child the primary outcomes are change from baseline to 12-months on sedentary time and minutes of moderate to vigorous activity per day and score on the Family Nutrition and Physical Activity tool (FNPA). In comparison to the Education Only group, we hypothesized that at 6, 12, and 18 months, families participating in the Health Coach group will demonstrate 1) a reduction in BMI for Index Adults, 2) an increase in minutes of moderate to vigorous physical activity and a decrease in sedentary time for both Index Adults and Index Children as measured by an accelerometer, and 3) a reduction in the number of obesity risk behaviors and an increase in the number of obesity prevention behaviors among Index Children as measured by the FNPA scale.

3. Participants

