Families were stratified (by recruitment site and self-identified race/ethnicity of the Index Adult) and randomized to the Health Coach group or the Education Only group in a 1:1 ratio by the Community Resource Specialist. A computer algorithm was used to randomize the families, and the Community Resource Specialist then discussed the results with the family and schedule the next step. Thus, Data Collectors were blinded to group assignment.

7. Study Conditions

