9.1. Power

Power calculations were based on data from the pilot intervention and information culled from related trials. See Table

Table 6. Power calculation	Standard deviations	Difference	80% power ^a	Assuming 30% dropout	Source
Adults BMI change	Intervention 2.29 ^b Control 2.28	1 kg/m ²	65 per group	92 per group	Wadden (2011) ¹³⁶
Adult Accelerometer	Intervention 101.9 ^c Control 77.7	35-minutes	82 per group	117 per group	Napolitano (2010) ¹³⁷
Children Accelerometer	59.4 for both ^d	30-minute	50 per group	71 per group	Robertson (2011) ¹³⁸
FNPA	5.1 for both ^e	2 points	81 per group	116 per group	Ihmels (2009) ¹¹⁹

^a Using a two-sided 0.05-level two-sample t-test

^b Pilot data at 6 months showed a SD 1.98 – We used Wadden's numbers to be conservative

^c The intervention group had baseline and 12-month SD's of 44.2 and 59.6, while the control group had SD of 42.5 and 44.6. No information was available on the SD of the baseline-to-12-month change. Taking the most conservative approach, we computed the largest possible pre-post SD and found the largest possible baseline-12 month SD's (101.9 intervention, 77.7 control)

^d Table 1 reported baseline-to-9 months CI's. From these, we computed a 0-9 month SD of 59.4 to use for the 0-12 month change

^e For those with income <\$25,000. Our pilot showed a similar number of SD 5.4 for change at 6 months

Based on these power calculations, a target of 260 families was to be recruited to account for dropout prior to randomization, following randomization, and throughout all timepoints of the intervention.

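### The primary t-test on 12-month change is valid, but a prespecified ANCOVA with baseline and the randomisation strata would usually be more precise, at almost no cost

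*Combined protocol and SAP*

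**What the plan says.** Section 2 defines the primary outcomes as changes: "For the Index Adult the primary outcomes are changes from baseline to 12-months", with child outcomes defined over the same interval. Section 9 follows suit: "The primary analysis compares the change in primary outcomes from baseline to 12 months between the treatment groups". The method is to "use two-sided t-test for the primary outcomes with multiple imputation to account for missing values". No covariate is named. Of the imputation, section 9 adds only that "Multiple imputation models will incorporate 6-month values when available". Mixed models are kept for other analyses, also without named covariates.

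Section 6 describes the 1:1 randomisation: "Families were stratified (by recruitment site and self-identified race/ethnicity of the Index Adult"). Neither factor reappears in section 9, and ANCOVA is mentioned nowhere.

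Table 6 in section 9.1 sizes the trial for a two-sample t-test and gives no baseline-to-12-month correlation. Footnote c supplies the only paired baseline and 12-month SDs: 44.2 and 59.6 for the intervention arm, "while the control group had SD of 42.5 and 44.6".

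**The concern.** A t-test on change is the baseline-adjusted model with the slope set to 1 in advance. When the true slope is below 1, as it commonly is for noisy measures, subtracting the whole baseline value adds noise. ANCOVA lets the data set the slope. Because the arms are randomised, both methods estimate the same treatment effect.

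Stratified randomisation balances the arms on site and race/ethnicity. If those factors predict outcome, an analysis that ignores them reports a standard error somewhat too large.

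What is at stake is the width of the confidence interval obtained from the same families, not the validity of the test.

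**Working it through.** **1. The plan's own figures.** Use n per group = 2(z_α + z_0.80)²s²/d², where s² is the mean of the two arm variances. For BMI, adult accelerometer, child accelerometer and FNPA:

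| | n per group |
|---|---|
| Stated in Table 6 | 65 / 82 / 50 / 81 |
| Two-sided 0.05, as footnote a says | 82 / 106 / 62 / 103 |
| One-sided 0.05 | 65 / 83 / 49 / 81 |

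The stated sizes match a one-sided test. At two-sided 0.05 they give about 69% to 71% power. This is a separate issue; all power figures below are two-sided.

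**2. Baseline term, general.** Let s0 and s12 be the SDs at baseline and 12 months.
- Change score variance: s0² + s12² − 2r·s0·s12.
- ANCOVA residual variance: s12²(1 − r²).
- With s0 = s12 = s these are 2s²(1 − r) and s²(1 − r²), so the ratio is (1 + r)/2. That is 0.75, 0.85 and 0.95 at r = 0.5, 0.7 and 0.9.

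With baseline in the model, analysing change or the 12-month value gives the same treatment coefficient, so the outcome definitions in section 2 stand.

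**3. Adult accelerometer, footnote c SDs** (common slope, same r in both arms).
- Mean baseline variance: (44.2² + 42.5²)/2 = 1879.9.
- Mean 12-month variance: (59.6² + 44.6²)/2 = 2770.7.
- Mean covariance: r(44.2×59.6 + 42.5×44.6)/2 = 2264.9r.
- Change score: 4650.6 − 4529.8r. ANCOVA: 2770.7 − 2728.7r².

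| r | pooled slope | change score | ANCOVA | ratio |
|---|---|---|---|---|
| 0.3 | 0.36 | 3291.7 | 2525.1 | 0.767 |
| 0.5 | 0.60 | 2385.7 | 2088.5 | 0.875 |
| 0.7 | 0.84 | 1479.7 | 1433.6 | 0.969 |
| 0.8 | 0.96 | 1026.7 | 1024.3 | 0.998 |

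The reductions are 23%, 12%, 3% and under 1%. The gain vanishes where the slope reaches 1, just above r = 0.8.

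**4. BMI.** At an assumed r of 0.9 to 0.95 the ratio is 0.95 to 0.975, a 5% to 2.5% reduction. With Table 6's change SD of about 2.285, such r values correspond to a baseline SD of roughly 5 to 7 (assumed), from r = 1 − 2.285²/(2s²).

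**5. FNPA illustration.** Difference 2; change SD 5.1 (assumed, since Table 6 does not say that 5.1 is an SD of change); equal SDs at both visits; completers only. ANCOVA SD = 5.1√((1 + r)/2); SE = SD√(2/n); exact noncentral t with 2n − 2 df (t-test) or 2n − 3 df (ANCOVA).
- Main case: the largest Table 6 row, 117 per group randomised, with 30% loss: 117 × 0.70 ≈ 82.
- Upper case: all 260 families randomised: 260 × 0.70/2 = 91.

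| | SD | power, n = 82 | 95% CI half-width, n = 82 | power, n = 91 |
|---|---|---|---|---|
| t-test on change | 5.10 | 70% | 1.57 | 75% |
| ANCOVA, r = 0.5 | 4.42 | 82% | 1.36 | 86% |
| ANCOVA, r = 0.7 | 4.70 | 77% | 1.45 | 81% |
| ANCOVA, r = 0.9 | 4.97 | 73% | 1.53 | 77% |

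**6. Strata terms, by simulation** (4,000 replicates per setting; layouts assumed, because the documents give no number of levels).
- Cost: with 182 families, 12 assumed cells and 5 df of main effects, strata of no prognostic value moved the mean SE from 0.6557 to 0.6564 (0.1%) at r = 0.5. With 164 families and 7 stratum terms, the variance ratio to the t-test was 0.756 with or without them.
- Benefit: in the 182-family layout, strata explaining 5% or 10% of residual variance lowered the mean SE from 0.6557 to 0.6393 or from 0.6559 to 0.6227, about 2.5% or 5%.
- Type I error: with strata explaining 15% (164 families), the t-test rejected in 3.2% to 3.3% of null runs and ANCOVA with strata in 4.7% to 4.9%. At 10% (182 families) the rates were 4.6% and 5.3%, with a Monte Carlo SE of about 0.3 points, which does not clearly show conservatism.

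**The case against.** The plan is coherent as written: outcomes, primary comparison and sample size are all framed as change, and the t-test is unbiased without type I error inflation. That stands, and it is why this is a recommendation rather than a defect.

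The size of the gain is uncertain. The larger reductions assume equal SDs, whereas the only paired SDs in the documents are unequal and give about half the gain at r = 0.5 and a fifth of it at r = 0.7. BMI gains little on any plausible r. This also stands, so a range is shown and no outcome is said to gain most.

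The sample available may be smaller than 91 per group, since section 9.1 says "a target of 260 families was to be recruited to account for dropout prior to randomization" as well as later loss. Hence 82 is the main case. At 82, ANCOVA reaches 80% power for FNPA at r = 0.5 but not at r = 0.7.

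The benefit of the strata terms is hypothetical. Section 4 describes more than four recruitment channels, and sparse levels would need combining. The low cost holds only for a modest number of levels.

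A reader might infer a correlation for FNPA by treating 5.1 as a cross-sectional SD and setting it beside footnote e, "Our pilot showed a similar number of SD 5.4 for change at 6 months", and then derive a sample-size saving. The documents do not support that. The 5.1 comes from an external low-income sample, the 5.4 from the pilot over 6 months, and two samples and a shorter interval do not identify a 12-month correlation.

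**Conclusion.** The point holds as a precision improvement. The planned test is valid but usually less precise than ANCOVA for the same effect, and ANCOVA is never materially worse. Depending on r and on whether the SDs are equal at the two visits, the variance reduction from baseline adjustment runs from under 1% to about 25% over the cases worked; for BMI it is about 2% to 5%. The FNPA powers rest on an assumed change SD of 5.1, equal SDs and completers only; imputation from 6-month values could raise power under either method. No accelerometer power is given, because Table 6 does not say whether those rows are activity or sedentary time. Any gain from the strata depends on their unknown prognostic value.

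Two stronger readings should be resisted. A reader might infer that the t-test is biased or wrong; nothing in the documents supports that. A reader might also take ANCOVA as a remedy for the one-sided sample sizes in Table 6; it is not, and that needs its own correction.

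**What to change.** Before any unblinded analysis, and by a documented SAP amendment:
- Prespecify for each primary outcome an ANCOVA of the 12-month value on arm, baseline value, recruitment site and race/ethnicity, as main effects.
- State a rule for combining sparse levels, fixed blind to outcome, such as a minimum count per level.
- Put the same terms in the imputation model. This matters most for the accelerometer outcomes, which have no 6-month measurement.
- Fit the model in each imputed dataset and pool by Rubin's rules.
- Keep the t-test on change as a sensitivity analysis.

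The cost is the amendment and the work of settling the strata levels. The variables are already collected, and no participants or visits are added. Section 4 describes recruitment in the past tense, and the documents do not show whether outcome data have been analysed by arm. If they have, the t-test should remain primary and the ANCOVA be reported as supportive.

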9.1. Power

Power calculations were based on data from the pilot intervention and information culled from related trials. See Table

Table 6. Power calculation	Standard deviations	Difference	80% power ^a	Assuming 30% dropout	Source
Adults BMI change	Intervention 2.29 ^b Control 2.28	1 kg/m ²	65 per group	92 per group	Wadden (2011) ¹³⁶
Adult Accelerometer	Intervention 101.9 ^c Control 77.7	35-minutes	82 per group	117 per group	Napolitano (2010) ¹³⁷
Children Accelerometer	59.4 for both ^d	30-minute	50 per group	71 per group	Robertson (2011) ¹³⁸
FNPA	5.1 for both ^e	2 points	81 per group	116 per group	Ihmels (2009) ¹¹⁹

^a Using a two-sided 0.05-level two-sample t-test

^b Pilot data at 6 months showed a SD 1.98 – We used Wadden's numbers to be conservative

^c The intervention group had baseline and 12-month SD's of 44.2 and 59.6, while the control group had SD of 42.5 and 44.6. No information was available on the SD of the baseline-to-12-month change. Taking the most conservative approach, we computed the largest possible pre-post SD and found the largest possible baseline-12 month SD's (101.9 intervention, 77.7 control)

^d Table 1 reported baseline-to-9 months CI's. From these, we computed a 0-9 month SD of 59.4 to use for the 0-12 month change

^e For those with income <\$25,000. Our pilot showed a similar number of SD 5.4 for change at 6 months

Based on these power calculations, a target of 260 families was to be recruited to account for dropout prior to randomization, following randomization, and throughout all timepoints of the intervention.

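### Table 6's sample sizes give about 70% power, not 80%, under the two-sided 0.05 t-test they are said to use

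*Combined protocol and SAP*

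**What the plan says.** Table 6 in section 9.1 gives, for four outcomes, the SDs of change, the target difference, a size per group for 80% power and a size inflated for 30% dropout. Footnote a states the test: "Using a two-sided 0.05-level two-sample t-test". The data analysis plan in section 9 agrees, saying the analysis will "use two-sided t-test for the primary outcomes with multiple imputation to account for missing values". Section 6 says families are "randomized to the Health Coach group or the Education Only group in a 1:1 ratio".

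The recruitment target is tied to the table: "Based on these power calculations, a target of 260 families was to be recruited". The same sentence says the target must also cover losses before randomisation, but gives no rate for them.

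**The concern.** The four sizes are too small for the test named in the footnote. They are about what a one-sided 0.05 test would need. If so, the power heading is wrong in every row, and so are the dropout-adjusted sizes and the basis for 260 families.

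What is at stake is how a null result is read. A reader who trusts the table would think that an effect of the planned size had a 20% chance of being missed. At the stated sizes the chance is about 30%. Type I error is not affected, because the planned analysis is two-sided.

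**Working it through.** **Inputs (Table 6).** Allocation is 1:1, alpha 0.05 and power 80%.

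| Outcome | SDs of change | Difference d | s1² + s2² | Stated n per group |
|---|---|---|---|---|
| Adult BMI | "Intervention 2.29 ^b Control 2.28" | 1 kg/m² | 10.4425 | 65 |
| Adult accelerometer | "Intervention 101.9 ^c Control 77.7" | 35 min | 16,420.9 | 82 |
| Child accelerometer | "59.4 for both ^d" | 30 min | 7,056.72 | 50 |
| FNPA | 5.1 in both groups | 2 points | 52.02 | 81 |

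**Step 1. Try to reproduce the stated sizes.** The normal approximation is n = (z + 0.8416)² (s1² + s2²) / d², with z = 1.960 for a two-sided and 1.645 for a one-sided 0.05 test. For FNPA, two-sided: (2.8016)² × 52.02 / 4 = 102.07. One-sided: (2.4865)² × 52.02 / 4 = 80.40. The exact sizes use the noncentral t distribution with 2n − 2 degrees of freedom and noncentrality d / √((s1² + s2²)/n).

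| Outcome | Stated | Two-sided, normal | Two-sided, exact t | One-sided, normal | One-sided, exact t |
|---|---|---|---|---|---|
| Adult BMI | 65 | 81.96 | 83 | 64.56 | 66 |
| Adult accelerometer | 82 | 105.21 | 107 | 82.88 | 84 |
| Child accelerometer | 50 | 61.54 | 63 | 48.48 | 50 |
| FNPA | 81 | 102.07 | 104 | 80.40 | 82 |

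No row fits the two-sided calculation. Every row is within 0 to 2 of the one-sided one. Unequal-variance degrees of freedom give the same exact sizes. Using one arm's SD alone does not rescue the two-sided reading across the rows.

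**Step 2. Power at the stated sizes.** For FNPA with n = 81, the standard error is √(52.02/81) = 0.801, the noncentrality is 2/0.801 = 2.50 and the two-sided critical value is 1.975, so power is 69.9%.

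| Outcome | Two-sided power | One-sided power |
|---|---|---|
| Adult BMI (65) | 69.7% | 79.9% |
| Adult accelerometer (82) | 69.1% | 79.3% |
| Child accelerometer (50) | 70.6% | 80.6% |
| FNPA (81) | 69.9% | 80.0% |

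**Step 3. Dropout column.** The inflation step is sound: 65/0.7 = 92.9, 82/0.7 = 117.1, 50/0.7 = 71.4 and 81/0.7 = 115.7, against the stated 92, 117, 71 and 116. The starting sizes are what is wrong. Corrected: 83/0.7 = 118.6, 107/0.7 = 152.9, 63/0.7 = 90.0 and 104/0.7 = 148.6, that is 119, 153, 90 and 149. The largest row rises from 2 × 117 = 234 to 2 × 153 = 306 randomised families, which is above 260.

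**Step 4. What 260 families give.** The loss before randomisation is not stated, so two cases are shown.
- *No loss before randomisation:* 130 per group × 0.7 = 91 completers.
- *About 10% loss (an assumption):* 260 × 0.9 = 234, or 117 per group; 117 × 0.7 = 81.9, about 82 completers.

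| Outcome | Power, 91 completers | Power, 82 completers | Detectable at 80%, 82 completers |
|---|---|---|---|
| Adult BMI | 84% | 80% (79.5%) | 1.01 kg/m² |
| Adult accelerometer | 74% | 69% | 39.9 min |
| Child accelerometer | 92% | 90% | 26.1 min |
| FNPA | 75% | 70% | 2.24 points |

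Footnote e gives a pilot FNPA change SD of 5.4. With that SD, FNPA power is 70% at 91 completers and 65% at 82.

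**The case against.** The arithmetic is not in dispute. The case on the other side concerns cause, consequence and inputs.

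- **Cause.** No single one-sided method reproduces all four rows exactly. A two-sided 0.10 test at 80% power, or a two-sided 0.05 test at about 70% power, gives the same sizes. This stands: the table cannot show which slip occurred. But each of these readings contradicts footnote a taken together with the 80% heading, so the correction is the same.
- **Conservative inputs.** Footnote c says the adult accelerometer SDs are upper bounds. If the baseline and 12-month values were uncorrelated (an assumption), footnote c's SDs give change SDs of √(44.2² + 59.6²) = 74.2 and √(42.5² + 44.6²) = 61.6. The two-sided test then needs 61 per group and has 90% power at 82. Likewise, footnote b's pilot BMI SD of 1.98 gives a need of 63 per group. These points stand as context. Real power may be higher for these two outcomes, and the FNPA shortfall is the firmer one. They do not repair a table that states its own SDs and is wrong for them. Nor do footnote c's figures yield the tabulated SDs: their maxima are 44.2 + 59.6 = 103.8 and 42.5 + 44.6 = 87.1, not 101.9 and 77.7.
- **Consequence.** One target serves all outcomes, and at that target BMI and child accelerometer are at or close to 80% or above it. This is correct, and the shortfall at the target is confined to adult accelerometer and FNPA.
- **Completers.** Counting completers ignores any gain from imputing with 6-month values. The documents give no basis for sizing that gain.
- **Timing.** Section 4 reports recruitment in the past tense, so no change to enrolment is in prospect. That limits the remedy to restating the figures. It does not make the stated power right.

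**Conclusion.** The concern holds. All four sizes in Table 6 are too small for the two-sided 0.05 t-test at 80% power that the plan specifies in both section 9 and section 9.1. On the table's own SDs and differences, they give 69% to 71% power. The correct sizes are 83, 107, 63 and 104 per group, or 119, 153, 90 and 149 with 30% dropout.

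At 260 families, the adult accelerometer (69% to 74%) and FNPA (70% to 75%) fall below 80% in both cases examined. BMI (80% to 84%) and child accelerometer (90% to 92%) do not fall materially short. The lower ends assume about 10% loss before randomisation, and the upper ends assume none. All figures assume 30% dropout afterwards and Table 6's SDs, which for the adult accelerometer were chosen as a pessimistic bound. A one-sided calculation is the likely origin, but this cannot be proved from the documents.

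**What to change.** 1. Keep the two-sided test. Moving to a one-sided test to match the table would weaken error control.
2. Correct Table 6 to 83 / 107 / 63 / 104 per group, and to 119 / 153 / 90 / 149 with 30% dropout.
3. Replace the sentence deriving 260 families from the table with what 260 families provide. Two-sided power is about 84% / 74% / 92% / 75% if all are randomised and about 80% / 69% / 90% / 70% at 82 completers per group, with the assumed loss before randomisation stated. The alternative is to give the differences detectable with 80% power at 82 completers: 1.01 kg/m², 39.9 min, 26.1 min and 2.24 points.
4. While correcting the adult accelerometer row, reconcile its SDs with footnote c and say that they are an upper bound. If pilot SDs are shown as a sensitivity check, show both the BMI and the FNPA values.

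The cost is a corrected table, a sentence or two, and a less favourable power statement. No extra participants are needed and the analysis does not change.

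### The adult accelerometer change SDs in Table 6 are called the largest possible but are not, and 82 per group does not follow from them at the stated two-sided level

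*Combined protocol and SAP*

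**What the plan says.** Section 9.1, Table 6, plans the adult accelerometer outcome for a 35-minute difference at 80% power, with change SDs given as "Intervention 101.9 ^c Control 77.7". The row gives 82 per group, or 117 per group allowing for 30% dropout.

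Footnote c explains the SDs. The source trial supplied only SDs at each time point: "The intervention group had baseline and 12-month SD's of 44.2 and 59.6, while the control group had SD of 42.5 and 44.6". It adds: "No information was available on the SD of the baseline-to-12-month change". The planners describe their approach as the most conservative one available: "we computed the largest possible pre-post SD and found the largest possible baseline-12 month SD's (101.9 intervention, 77.7 control".

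Footnote a gives the test for the whole table: "Using a two-sided 0.05-level two-sample t-test". Section 9 (Data Analysis Plan) agrees, since the analysis will "use two-sided t-test for the primary outcomes". Section 2 lists adult accelerometer activity among the primary outcomes.

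**The concern.** Two statements about this row can be checked against the footnotes' own numbers, and both fail.

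First, an upper bound on the SD of a change follows directly from the two component SDs. The stated values fall below it, by different proportions in the two arms, so either the description or at least one of the six figures is wrong.

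Second, the row's sample size is smaller than its own SDs, difference, power and test require.

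At stake is the planning basis for a primary outcome. A reader is told that 80% power was secured under a worst-case SD, and neither part can be recovered from the footnotes. The row also has the largest sample size in the table (117 per group after dropout, against 116 for FNPA). Section 9.1 bases the 260-family target on the table as a whole, without saying which row drives it.

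**Working it through.** **Inputs (section 9.1, Table 6 and footnotes a and c).** Difference 35 minutes; 80% power; two-sided 0.05 two-sample t-test; dropout 30%. Stated change SDs 101.9 (intervention) and 77.7 (control). Component SDs 44.2 and 59.6 (intervention), 42.5 and 44.6 (control). Allocation is 1:1 (section 6).

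**1. The maximum SD of change.** With component SDs *a* and *b* and correlation *r*, SD(change) = √(a² + b² − 2rab). This is largest at r = −1, where it equals a + b.

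| Arm | Stated | Maximum a + b | Shortfall | r implied by stated SD |
|---|---|---|---|---|
| Intervention | 101.9 | 44.2 + 59.6 = 103.8 | 2% | −0.93 |
| Control | 77.7 | 42.5 + 44.6 = 87.1 | 11% | −0.59 |

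The implied correlation is (a² + b² − s²)/(2ab). Rounding cannot explain the gap: if each component were 0.05 lower, the maxima would still be 103.7 and 87.0. The stated values are feasible, but they are not maxima and do not correspond to one common correlation.

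**2. Reproducing 82 per group from the stated SDs.** Normal approximation: n = (s₁² + s₂²)(z_α + z_0.80)²/δ². Here s₁² + s₂² = 101.9² + 77.7² = 16,420.9 and δ² = 35² = 1,225.

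- Two-sided 0.05: 16,420.9 × 7.849 / 1,225 = 105.2, so 106. By exact (noncentral) t, 107.
- One-sided 0.05: 16,420.9 × 6.183 / 1,225 = 82.9, so 83. By exact t, 84.
- Replacing the pooled variance by the simple mean of the two SDs (89.8), one-sided: 2 × 89.8² × 6.183 / 1,225 = 81.4, so 82.

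The stated 82 is therefore close to a one-sided calculation and far from a two-sided one. The dropout step is sound: 82/0.7 = 117.1.

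**3. Other rows, as a check on the one-sided reading (exact t).**

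| Row | Stated n | One-sided | Two-sided |
|---|---|---|---|
| Adult BMI | 65 | 66 | 83 |
| Adult accelerometer | 82 | 84 | 107 |
| Child accelerometer | 50 | 50 | 63 |
| FNPA | 81 | 82 | 104 |

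**4. Size of each effect (exact t, 35 minutes).**

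| SDs | n, two-sided | After 30% dropout | Power at 82, two-sided | Detectable difference at 82 | n, one-sided | Power at 82, one-sided |
|---|---|---|---|---|---|---|
| 101.9 / 77.7 | 107 | 107/0.7 → 153 | 69% | 39.9 min | 84 | 79% |
| 103.8 / 87.1 | 119 | 119/0.7 = 170 | 64% | 42.2 min | 94 | 75% |

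Of the gap 119 − 82 = 37 per group, 119 − 107 = 12 come from the SDs. The other 107 − 82 = 25 come from the mismatch with the two-sided level, and of these about 2 (84 − 82) are not explained by sidedness.

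**5. Other correlations, same component SDs, two-sided.** The documents give no correlation, so each *r* is an assumption.

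| r | Change SDs | n per group | Power at 82 |
|---|---|---|---|
| 0 | 74.2 / 61.6 | 61 | 90% |
| 0.3 | 62.7 / 51.6 | 44 | 97% |
| 0.5 | 53.6 / 43.6 | 32 | 99.5% |
| 0.7 | 42.6 / 33.8 | 20 | >99.9% |

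**6. At the recruitment target.** If all 260 families were randomized 1:1 and 30% dropped out, 260/2 × 0.7 = 91 per group would remain. Two-sided power is then 74% with the stated SDs, 69% at the maxima and 93% at r = 0.

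**The case against.** The strongest reply is that the SD error has little practical weight. It matters only at strongly negative correlations between a person's baseline and 12-month activity, which is a bound and not a realistic planning value. The stated SDs are well above the zero-correlation values of 74.2 and 61.6, so the row remains cautious on SD. That stands, and it is why this point makes no claim of underpowering. It does not rescue the statement that these are the largest possible values, and the reassurance rests on a correlation the plan never gives.

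Second, the larger part of the discrepancy is the one-sided/two-sided mismatch, and it is not particular to this row. This is correct: all four rows sit near the one-sided figures. It makes the mismatch harder to dismiss, and correcting this row alone leaves the other three. One-sidedness is still an inference, since neither 83 nor 84 is exactly 82.

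Third, the component SDs come from a source not available here. One of them may be mistranscribed while 101.9 and 77.7 are right, so 103.8 and 87.1 are maxima only if the components are correct. That also stands.

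Finally, the plan describes recruitment in the past tense, the 260 target also covers loss before randomization, and the analysis is by intention to treat with multiple imputation. The powers at 91 per group are therefore illustrative, and a correction cannot alter enrolment. It can still correct what the plan claims.

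**Conclusion.** The concern holds on both counts. On footnote c's own components, the maximum change SDs are 103.8 and 87.1, so 101.9 and 77.7 are not the largest possible. The derivation is not shown, so the cause is unknown. With the stated SDs and footnote a's test, 80% power needs 107 per group, not 82, and 82 gives 69%. At the maxima the figures are 119 and 64%.

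The mismatch in test level accounts for about two thirds of the total gap (25 of 37 per group) and does not depend on the SD question or on any correlation. The SD part is conditional on the printed components being right. Nothing here shows that the trial lacks power for this outcome: under a correlation of 0 or above, 82 per group gives at least 90% two-sided power. What fails is the row's stated basis and its reproducibility.

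**What to change.** Check the four component SDs and the two derived SDs against the source. Then take one of two routes.

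1. **Preferred.** Drop the claim that the SDs are the largest possible and give a range, with the correlation stated as an assumption. For r = 0 to 0.7 the change SDs run from 74.2/61.6 down to 42.6/33.8 and the requirement from 61 down to 20 per group, with at least 90% power at 82.
2. Keep the bound and state it correctly: 103.8 and 87.1, 119 per group, 170 after dropout, 64% power at 82.

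In either case, restate the row's sample size and power at footnote a's two-sided 0.05 level. Check the other three rows of Table 6 for the same mismatch at the same time.

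The cost is one corrected footnote and one table row. Design, enrolment and the primary analysis do not change.
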